2.3 Rationale

2.3.1 Combination Therapy using CDX-1127 (Varlilumab) and Nivolumab in Hematological Malignancies

Malignant cells are able to escape immune surveillance by co-opting cellular mechanisms such as immune checkpoint pathways (Green *et al.*, 2010; Dong *et al.*, 2002; Wilcox *et al.*, 2009) or inducing T-cell exhaustion (Yang *et al.*, 2014; Yang *et al.*, 2015; Yang *et al.*, 2012). These immune checkpoints are natural control mechanisms that prevent T-cell hyperactivation following an antigenic challenge (Keir *et al.*, 2008; Francisco *et al.*, 2010). The programmed death 1 (PD-1) pathway is an immune checkpoint with a clearly established role in tumor-mediated immunosuppression. Some neoplastic cells are able to express cognate ligands (PD-L1 and PD-L2) that are recognized by the PD-1 receptor expressed on the surface of activated effector T-cells. Activation of the PD-1: PD-L1/2 axis leads to a cascade of intracellular events that result in decreased T-cell survival and function. Monoclonal antibodies that recognize the PD-1 receptor are able to block its interaction with the ligands and result in release of an effective anti-tumoral immune response. Nivolumab is a fully human immunoglobulin G4 (IgG4) with high affinity against the PD-1 receptor with anti-tumoral activity against a number of solid tumors and hematological malignancies (OPDIVO Package Insert, 2014).

The single-agent safety and efficacy of nivolumab in hematological malignancies has been evaluated in a phase I dose-escalation study (NCT01592370). Patients with advanced hematological malignancies received nivolumab at a dose of 1 mg/kg with escalation to 3 mg/kg. Since the maximum tolerated dose (MTD) was not reached, patients in the expansion cohorts received 3 mg/kg at week 1, week 4, and then every 2 weeks. Results from the expansion cohort that included 23 patients with advanced classic Hodgkin lymphoma (CHL) have now been published (Ansell *et al.*, 2014). Nivolumab was safe and well tolerated in this patient population and yielded an objective response in 20 patients (ORR 87%). Results from the experience in a small cohort of non-Hodgkin lymphoma (NHL) and other hematological malignancies demonstrated limited single agent activity in B-cell NHL (ORR 26%) multiple myeloma (ORR 4%), and T-cell NHL (ORR 17%) (Lesokhin *et al.*, 2016). T-cell exhaustion has been recognized as another important mechanism by which lymphoma cells escape an immune attack. Our group has demonstrated that the tumor microenvironment in NHL produces profound immunosuppression mediated by regulatory T-cells (T_{reg}) (Yang et al., 2006a; Yang et al., 2006b; Yang et al. 2007; Yang et al., 2009; Ai et al., 2009; Hilchey et al., 2007) and suppressive monocytic cells (SMC) (Wilcox et al., 2009; Xiu et al., 2015). Strategies aimed at reversing T-cell exhaustion using agonistic molecules have the potential to produce an effective anti-tumoral response. The co-stimulatory molecule CD27 is constitutively expressed in many normal immune cells including T-cells, B-cells and NK cells van de Ven et al., 2015). T-cell function and survival is enhanced once CD27 binds to its ligand (CD70) on the surface of antigen presenting cells in the context of T-cell receptor engagement. Pre-clinical studies demonstrated that immune tolerance and exhaustion might be prevented or reversed by signaling through CD27. CDX-1127 (Varlilumab) is an agonistic IgG1 monoclonal antibody that recognizes CD27 (He et al., 2013; Vitale et al., 2012; Thomas et al., 2014). CDX-1127 (Varlilumab) has also demonstrated direct anti-tumoral activity in xenograft models of human lymphoma and leukemia cell lines via antibody-dependent cellmediated cytotoxicity (ADCC). Given that CD27 expression has been demonstrated in many hematological malignancies (Dong et al., 2002), this constitutes another potential mechanism by which CDX-1127 (varlilumab) may enhance tumor eradication.

A phase 1 study evaluated the safety, tolerability and efficacy of single-agent CDX-1127 (varlilumab) in patients with advanced hematologic malignancies (NCT01460134) (Ansell et al., 2014). In the dose-escalation phase, patients received CDX-1127 (varlilumab) in 5 dose-levels ranging from 0.1 to 10 mg/kg IV weekly. A total of 24 patients with advanced hematological malignancies received single-agent CDX-1127 (varlilumab) given as a single dose followed by a 28-day observation period that was then followed by a multi-dose period consisting of 4 weekly doses followed by a 4-week observation period. Retreatment with up to 4 additional cycles (4 weekly doses followed by 8-week observation period) was allowed for patients with stable disease. No doselimiting toxicity (DLT) was observed and MTD was not reached. Treatment-related adverse events were infrequent and nearly all mild to moderate in severity. No overlapping in toxicity with checkpoint inhibitor blockade therapy (endocrinopathies, colitis, and pneumonitis) was observed. The half-life of CDX-1127 (varlilumab) ranged from 6 days (at 1 mg/kg) to 10.6 days (at 10 mg/kg) with linear pharmacokinetics. One patient experienced a complete response (patient with heavily pretreated Hodgkin lymphoma treated at the 0.3 mg/kg dose-level) and 3 patients with NHL had stable disease with duration of response up to 14 months. Correlative studies demonstrated that treatment with CDX-1127 (varlilumab) was associated with reduction of circulating Treg and increase in pro-inflammatory cytokines.

The preliminary results of a phase 1 dose-escalation study combining CDX-1127 (varlilumab) and nivolumab in advanced solid malignancies were recently released (Sanborn *et al.*, 2016). A total of 35 patients with advanced solid tumors (colorectal cancer, melanoma, gynecological cancers and head/neck cancers) were treated with escalating doses of CDX-1127 (varlilumab) (0.1, 1.0 & 10 mg/kg) in combination with nivolumab (3 mg/kg) every 2 weeks for 4 doses. Repeat treatments with combination therapy were permitted for 4 additional cycles in patients deriving clinical benefit (stable

disease or better). Therapy was well tolerated and MTD was not reached. Correlative studies demonstrated increase in inflammatory cytokines, decrease in circulating CD4+ and regulatory T-cells as well as increase in tumor-infiltrating lymphocytes.

We hypothesize that combination therapy using a PD-1 inhibitor (nivolumab) and a CD27 agonist (CDX-1127; varlilumab) in patients with advanced hematological malignancies is safe and produces a synergistic effect compared to single-agent nivolumab. To test this hypothesis we propose a randomized phase 2 trial comparing single-agent immunotherapy using nivolumab versus dual immunotherapy (CDX-1127 (varlilumab) and nivolumab) in patients with relapsed or refractory aggressive B-cell NHL. Primary endpoint is response rate and patients in the control arm (nivolumab alone) would be allowed to cross over to the combination arm at the time of progression.

2.4 Correlative Studies Background

- 2.4.1 Integrated Biomarkers
- 2.4.1.1 Quantification and Characterization of CD27+ Cells in the Tumor Microenvironment by Immunohistochemistry (IHC)

The costimulatory molecule CD27 is a member of the tumor necrosis factor (TNF) receptor superfamily, and is constitutively expressed on the majority of mature T-cells, memory B cells, and a portion of natural killer cells. The interaction of CD27 with its ligand (CD70) plays key roles in activation, proliferation and survival processes of different immune cells. CD27 expression is also present on most B-cell malignancies at varying levels. It is therefore postulated that CDX-1127 (varilumab) - an agonist anti-CD27 monoclonal antibody – may exert its anti-tumor activity through activation of CD27-expressing T-cells in the context of T cell receptor stimulation and also through direct cytotoxic activity on tumor cells expressing CD27.

We therefore hypothesize that the expression of CD27 in the tumor cells and/or on its surrounding microenvironment is required for CDX-1127's (varlilumab's) antitumoral activity. We further hypothesize that the level of expression of CD27 along with its localization (tumor cells vs. immune cells) may serve as a predictive biomarker for the activity of CDX-1127 (varlilumab) in patients with B-cell lymphomas. To test this hypothesis we will assess CD27 expression level and localization by IHC on tumor biopsies obtained at the time of registration from patients treated under this protocol. CD27 expression will not be required for participation in the study (integral biomarker). The level of CD27 expression along with its localization (tumor cells vs. immune cells) will be compared between patients who achieve clinical benefit from treatment with CDX-1127 (varlilumab). For patients in group 1 (nivolumab single-agent) who agree to undergo a repeat biopsy to confirm progression of disease and then cross over to group 2 (combinatory therapy with CDX-1127 (varlilumab) and nivolumab), the CD27 IHC assay will be repeated and compared to baseline.

The CD27 expression evaluation via IHC will be performed centrally by Mosaic Laboratories, L.L.C. ([name]) using a proprietary assay using the rabbit mAb clone EPR8569 from Abcam. CD27 staining will be evaluated by image analysis using an Aperio image analysis algorithm and the final score will be expressed as % of cells at 0 (unstained), 1+, 2+ and 3+, in addition to number of CD27+ cells/mm2. Validation report can be provided upon request.

- 2.4.2 Exploratory Biomarkers
- 2.4.2.1 Comprehensive Analysis of Immune Cell Subpopulations using Mass Cytometry (CyTOF)

CyTOF (cytometry at time-of-flight) or mass cytometry is a new single-cell proteomics platform that uses mass spectrometry to evaluate more than 45 simultaneous parameters on a single-cell level (Bendall *et al.*, 2012). This technology uses nonradioactive non-biological isotopes as reporters tagged to antibodies. Measurements are based on mass spectrometry, which largely avoids the hurdles of interference and spectral overlap seen with standard fluorescence-based flow cytometry. CyTOF is an ideal platform for the study of the tumor microenvironment given its ability to assess a large number of simultaneous parameters and resolve small differences in a heterogeneous population of cells. Taking advantage of the simultaneous assessment of several parameters per cell, CyTOF retains the ability to quantitate main lineage subsets in samples as small as 100,000 cells (Yao *et al.*, 2015). This is particularly useful in situations where cell count is limited - such as tumor biopsies - or in the assessment of rare immune cell subsets.

CyTOF is therefore a powerful tool to study a complex biological system such as the microenvironment of B-cell lymphomas, especially in the context of a study using immune modulating drugs. Since both Nivolumab and CDX-1127 (varlilumab) may have a broad range of effects on different populations of cells – including tumor cells and host immune cells – an assay that simultaneously characterize these effects is necessary. The CyTOF assays will be performed on two different specimen types: (1) single-cell suspensions created from tumor samples obtained at the time of registration and at the time of treatment cross over (for patients in group 1) and on (2) peripheral blood mononuclear cells (PBMC) obtained before the infusion of the study drugs during the first 24 weeks of treatment.

Unstimulated specimens will be stained using a custom-designed 34-parameter global phenotyping panel recognizing 36 surface proteins and acquired on CyTOF2TM. EQTM Four Element Calibration Beads (Fluidigm) will be used for instrument calibration and normalization between experiments. Cisplatin (195Pt) will be used as a cell viability marker. The primary assay will allow identification of major immune cell populations (T-cells, B-cell, NK cell, monocyte/macrophages) along with detailed characterization of T-cell subsets (cytotoxic, regulatory, helper 1, helper 2,

helper 9, helper 17, helper 22, follicular helper, central memory, effector memory, naïve) and separately evaluate them for expression of markers of T-cell exhaustion (PD-1, LAG-3, TIM-3) and expression of co-stimulatory molecules (CD27, CD28, ICOS). Specimens with a surplus of cells will also be stained in parallel with a separate 22-parameter phenotyping panel recognizing surface and intracellular proteins in order to detail the phenotype of monocyte/macrophage subpopulations. See section 9.3 for details on the CyTOF assay panels. Analysis of immune cell subsets will be largely exploratory and reported descriptively.

2.4.2.2 Identification and Characterization of Intratumoral Immune Cells by Immunohistochemistry (IHC)

Expression of PD-L1 has been demonstrated to associate with clinical response of cancer patients treated with nivolumab. It is also postulated that CD8+ cytotoxic T-cell infiltration is critical to mediate anti-tumoral immunity in the context of PD-1 blockade. In the phase 1 trial dose-escalation study combining nivolumab with CDX-1127 (varlilumab) there was an increase in tumor-infiltrating lymphocytes (TILs) at all CDX-1127 (varlilumab) dose-levels. A trend towards increase in PD-L1 expression and CD8+ TILs was observed in patients with stable disease or better responses. Therefore, multiple markers including T cell, tumor cells, as well as related co-stimulatory and inhibitory markers will be stained to identify if there is any association of expression of these markers with the clinical activity of the study drugs.

Serial 4-µm paraffin-embedded sections will be used for IHC. The tissue will be deparaffinized with three changes of xylene and cleared through graded series of ethanol. Endogenous peroxidase will be quenched by incubation in 50% methanol/H2O2 and after rinsing with tap water; all sections will be pretreated for 30 minutes with 50 mmol/L EDTA using a steamer and cooled for additional 5 minutes. All staining will be done automatically on DAKO Autostainer using the following antibodies to CD11c (Leica Microsystems 5D11), CD14 (Cell Marque EPR 3653), CD163 (DAKO 1F8), CD68 (DAKO PG-M1), CXCL13 (R&D Systems 53610), FOXP3 (Abcam 236AE/7), CD3 (R&D Systems), PD-L1 (405.9A11), PD-L2 (366C.9E5), CD8a (Dako M7103) and PD-1 (Abcam NAT). The sections will be viewed with an Olympus BXFA51 microscope and pictures taken with an Olympus DP71 camera. Stained slides will be scored by expert hematopathologist. Analysis of intra-tumoral immune cell subsets by IHC will be largely exploratory and reported descriptively.

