1.3 Exploratory Objectives

- 1.3.1 To determine the effect of combination therapy with CDX-1127 (varlilumab) and nivolumab on the immune system as assessed by immunohistochemistry (IHC), mass cytometry (CyTOF), changes in serum cytokine profile and immunogenicity assays.
- 1.3.2 To describe the pharmacokinetic profile of CDX-1127 (varlilumab) and nivolumab when used in combination.

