A tissue cross-reactivity study was performed with observed tissue binding of CDX-1127 (varlilumab) being similar between human and Cynomolgus macaque tissues. Highly specific CDX-1127 (varlilumab)-FITC staining of mononuclear cells was observed and attributed to staining of target CD27 at the membrane and in the cytoplasm of these cells in human and Cynomolgus monkey tissues. Unexpected staining was observed in Cynomolgus monkey pituitary epithelium, but was restricted to the cytoplasm and did not correlate with any findings in the toxicology study. As a consequence of that, and the lack of such binding in human tissues, it is unlikely to be of clinical relevance.

A phase I study evaluated the safety, tolerability and efficacy of single-agent CDX-1127 (varlilumab) in patients with advanced hematologic malignancies (NCT01460134; Ansell et al, 2014). In the dose-escalation phase, patients received CDX-1127 (varlilumab) in 5

dose-levels ranging from 0.1 to 10 mg/kg IV weekly. A total of 24 patients with advanced hematological malignancies received single-agent CDX-1127 (varlilumab) given as a single dose followed by a 28-day observation period that was then followed by a multi-dose period consisting of 4 weekly doses followed by a 4-week observation period. Retreatment with up to 4 additional cycles (4 weekly doses followed by 8-week observation period) was allowed for patients with stable disease. No dose-limiting toxicity (DLT) was observed and MTD was not reached. Treatment-related adverse events were infrequent and nearly all mild to moderate in severity. No overlapping in toxicity with checkpoint inhibitor blockade therapy (endocrinopathies, colitis and pneumonitis) was observed. The half-life of CDX-1127 (varlilumab) ranged from 6 days (at 1 mg/kg) to 10.6 days (at 10 mg/kg) with linear pharmacokinetics. One patient experienced a complete response (a patient with heavily pretreated Hodgkin lymphoma treated at the 0.3 mg/kg dose-level) and 3 patients with NHL had stable disease with duration of response up to 14 months. Correlative studies demonstrated that treatment with CDX-1127 (varlilumab) was associated with reduction of circulating Treg and increase in pro-inflammatory cytokines.

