Generally we strongly encourage early evaluation while withholding drug, and appropriate treatment as indicated in the management tables and event specific guidelines.

Dose hold = All study drugs must be held. Day 1 of the next cycle is given when the patient meets the protocol criteria to restart drugs. The current cycle will include all days until the patient resumes treatment and may be longer than 28 days.

ALL OTHER EVENTS	Management/Next Dose	
≤ Grade 1	No change in dose	

ALL OTHER EVENTS	Management/Next Dose
Grade 2	Hold until \leq Grade 1 OR baseline (exceptions as noted below)
Grade 3	Off protocol therapy (exceptions as noted below)
Grade 4	Off protocol therapy
Recommended management: As clinically indicated	

• Any grade 2 drug-related uveitis or eye pain or blurred vision that does not respond to topical therapy and does not improve to Grade 1 severity within the retreatment period OR requires systemic treatment should go off protocol treatment

- Any adverse event, laboratory abnormality, or intercurrent illness which, in the judgment of the investigator, presents a substantial clinical risk to the subject with continued study drug dosing should go off protocol treatment.
- Any grade 3 or 4 drug-related laboratory abnormality or electrolyte abnormality, that can be managed independently from underlying organ pathology with electrolyte replacement, hormone replacement, insulin or that does not require treatment **does not** require discontinuation.
- Lymphopenia is an expected event for both study drugs. Asymptomatic lymphopenia does not constitute reason to hold or discontinue the study drugs, regardless of the grade

Skin Rash and Oral Lesions	Management/Next Dose
≤ Grade 1	No change in dose *
Grade 2	Hold* until $1 \le$ Grade resolved. Resume at same dose level.
Grade 3	Hold* until \leq Grade 1. Resume at same level at investigator discretion
Grade 4	Off protocol therapy
*Patients with purpuric or bullous lesions must be evaluated for vasculitis, Steven-Johnson syndrome, TEN, and autoimmune bullous disease including oral lesions of bullous pemphigus/pemphigoid. Pruritus may occur with or without skin rash and should be treated symptomatically if there is no associated liver or GI toxicity. Note skin rash typically occurs early and may be followed by additional events particularly during steroids tapering.	
Recommended management: AE management guidelines	

Liver Function	
AST, ALT,	Management/Next Dose
Bilirubin	

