c.	A pre-study biopsy is mandatory for all groups and must be obtained within 60 days prior to registration. For Group 1 patients who elect to cross over to Group 2, a biopsy is mandatory at that time. An off-study biopsy is optional for all groups.
d:	Off-study evaluation to be performed 30 days (+/- 14 days) after the last dose of study drug. Patients are followed for at least 100 days for AE assessment.
e:	As clinically indicated, perform an evaluation of cardiac function including ECG and echocardiogram for any patients with a history of CHF or at risk because of underlying cardiovascular disease or exposure to cardiotoxic drugs. Also perform an evaluation for patients with evidence of CHF, MI, cardiomyopathy, or myositis including lab tests and cardiology consultations including ECG, echocardiogram, CPK and troponin.
f:	Blood draw for correlative studies will be obtained at baseline (within 14 days prior to start of protocol therapy) and within 72 hours prior to the administration of any of the study drugs on dosing days. These blood draws may be performed at the same occasion as other laboratory tests obtained for the purpose of clinical monitoring of the patient. Patients who cross-over from Group 1 to Group 2 will need 4 additional blood draws pre-dose prior to their first 4 infusions of CDX-1127 (varlilumab) for immunogenicity and PK studies.
g:	A serum or urine pregnancy test is required within 24 hours of starting study treatment. If the pre-study assessment was performed within 24 hours prior to start of study treatment, a pregnancy test does not need to be repeated.
*:	Starting with Cycle 5 (Week 17), the dosage and administration schedule of nivolumab is changed to 480 mg every 4 weeks. The dosage and administration schedule of CDX-1127 (varlilumab) remains unchanged. Once the schedule of administration of nivolumab changes, the frequency of routine evaluations also changes accordingly to every 4 weeks as

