13.5 Analysis of Exploratory Endpoints

To determine the effect of combination therapy with CDX-1127 (varlilumab) and nivolumab on the immune system as assessed by immunohistochemistry (IHC), mass cytometry (CyTOF) and changes in serum cytokine profile, multiple measures will be evaluated. For each measure below, baseline values and changes in these parameters over time will be both graphically and quantitatively summarized and explored. Standard paired comparisons methodologies (Wilcoxon signed rank and McNemar's tests) will be used to assess changes in these variables before and after therapy. In addition, baseline values and changes over time in each measure will be explored in relation to clinical outcome. Differences between responders and non-responders will be assessed using Wilcoxon's rank sum (continuous data) or Fisher's exact (categorical data) test. The relationship between each measure and time to event measures (PFS, OS) will be evaluated using Cox's proportional hazards models and log-rank tests.

CD27 IHC: CD27 expression will be evaluated in terms of level (an ordinal • variable such as low, medium, high), % of cells expressing, and location (expression in tumor cells vs. expression in normal immune cells). The expression level can be gathered continuously and may also be evaluated as a categorical variable (low, medium, high expression for example). These values will be evaluated as predictors of response. This is the only integrated biomarker. The expression level of CD27 will be analyzed using the "marker-by-treatment predictiveness curves" in Janes et al. to explore CD27 as a potential predictive biomarker for the benefit of Varlilumab. Specifically, we will display the response rate as a function of the percentiles of CD27 for each treatment arm: Varlilumab plus Nivolumab and Nivolumab alone. We will use logistic regression to model the response rate as a function of treatment and CD27 (as a continuous variable). The distribution of CD27 will be estimated empirically in the entire trial population and used to calculate CD27 values corresponding to each fixed percentile. If the two predictiveness curves cross (suggesting predictive potential of CD27), the point where the two curves cross would be a possible choice of threshold for dichotomizing CD27 into "low" versus "high". Threshold levels

shown to be best predictors of clinical outcomes will be considered as reference for later pivotal trials.

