- Analysis of Peripheral Blood Immune cells by Mass Cytometry (CyTOF): The patient's peripheral blood will be evaluated serially (at baseline and every 14 days for the first 12 weeks on study). The assay will detect and quantify the presence of specific subpopulations of immune cells (expressed as % of parent). In this exploratory analysis the relationship between presence/absence of a particular subtype of cell and association with outcomes will be evaluated. Evaluation of particular combinations of immune cells (immune signature) and whether they are predictive of outcome will also be evaluated.
- Identification/Characterization of Intratumoral Immune cells by IHC and CyTOF: Immune cell subpopulations in the neighborhood around the tumor will be evaluated with this assay. This is similar to above (CyTOF on peripheral blood) but in this case the assessment is made on the tumor biopsy specimen. The presence/absence of different subsets will be identified and quantified and the association with clinical outcomes will be evaluated as specified above. This is another exploratory biomarker.
- Evaluation of Genetic Alterations of Chromosome 9p24.1 by FISH: This chromosomal region will be evaluated and patients will be categorized in 4 groups: normal, amplified, relative copy gain or polysomy. The proportion of patients in each of these groups who achieve a response will be evaluated. This is another exploratory biomarker.
- Evaluation of Serum Cytokine Profile by ELISA: Serially collected peripheral blood (at baseline and every 14 days for the first 12 weeks on study) will be analyzed. The levels (continuous variable) of 30 different cytokines will be assessed at each of those time points. The elevation or decrease in any individual cytokine or a combination of them will be explored, as well as the association with outcomes. This is another exploratory biomarker.
- Evaluation of Mutation Burden by WES: Tumor tissue will undergo whole-exome sequencing to determine if the amount of mutations (continuous) is associated with outcome. This is another exploratory biomarker.

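### Blood CyTOF subsets are planned only as percent of parent; adding derived cells per microlitre from the scheduled CBC would separate subset loss from a shift in composition

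*Combined protocol and SAP*

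**What the plan says.** Exploratory objective 1.3.1 asks what the combination does "on the immune system as assessed by immunohistochemistry (IHC), mass cytometry (CyTOF), changes in serum cytokine profile and immunogenicity assays". For CyTOF, Section 2.4.2.1 lists what the panel will read: "The primary assay will allow identification of major immune cell populations (T-cells, B-cell, NK cell, monocyte/macrophages) along with detailed characterization of T-cell subsets". That sentence names the populations but gives no scale.

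The scale is in the peripheral blood bullet of Section 13.5, where the assay is to quantify "specific subpopulations of immune cells (expressed as % of parent". The bullet also mentions presence or absence of a cell type. The opening paragraph of Section 13.5 says that for each measure "baseline values and changes in these parameters over time will be both graphically and quantitatively summarized and explored". It plans Wilcoxon signed rank and McNemar tests for change, responder versus non-responder comparisons, and Cox models and log-rank tests for PFS and OS.

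On what to expect in blood:
- Section 2.3.1, varlilumab plus nivolumab in 35 patients with solid tumors: "decrease in circulating CD4+ and regulatory T-cells".
- Section 2.2.1, varlilumab alone in 24 patients with hematologic malignancies: treatment "was associated with reduction of circulating Treg and increase in pro-inflammatory cytokines".
- Section 6.1: "Lymphopenia is an expected event for both study drugs".

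On what is collected: Study Calendar footnote a schedules a CBC with differential in the 72 hours before each study drug administration. Footnote f sets the same 72-hour window for correlative blood and adds: "These blood draws may be performed at the same occasion as other laboratory tests".

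**The concern.** A percent of parent is a ratio. It describes composition and carries no information on how many cells circulate. If a drug lowers the parent population as well as the subset, the ratio cannot tell depletion from a shift in mix.

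A moving denominator is foreseeable here. The protocol expects lymphopenia with both drugs. It cites lower circulating CD4+ cells with the combination, and CD4+ cells are a natural parent for Treg. Section 2.2.1 also places CD27, the target of varlilumab, on most mature T cells, so the target sits on the parent as well as on the subset.

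At stake is how well objective 1.3.1 is answered. Run on percent of parent alone, the paired tests and outcome associations could describe a subset as stable or raised while its circulating number fell. The protocol already uses two scales for its tissue marker: Section 2.4.1.1 scores CD27 both as a percentage of cells and as cells per mm². Blood CyTOF has no such counterpart.

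**Working it through.** The plan states no figure on this point, so there is none to reproduce. The check has four parts.

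**1. Is there any other unit?** Sections 2.4.2.1, 9.3.1.3 and 13.5 give none for blood subsets. Under Section 9.3.1.3 the sample is gradient-separated, frozen mononuclear cells. The beads are for calibration and normalization. No counting step relates events to blood volume, and no step links CyTOF fractions to the CBC. Presence or absence does not recover a count.

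**2. How percent of parent behaves.** Let the subset fall by a fraction s and its parent by p. Then

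follow-up % = baseline % × (1 − s)/(1 − p),

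and the relative change is (p − s)/(1 − p). It is zero when s = p, positive when the parent falls more, and negative only when the subset is lost preferentially.

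The documents give no counts or effect sizes, so these are assumptions. Baseline per µL: lymphocytes 1200, CD3 900, CD4 500, Treg 30. Hence CD4 is 500/900 = 55.6% of CD3, and Treg is 30/500 = 6.0% of CD4.

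| Assumed falls | True count | Percent of parent |
|---|---|---|
| (a) CD4 50%, Treg 50% | Treg 30 to 15 | 6.0 × 0.5/0.5 = 6.0% (flat) |
| (b) CD4 50%, Treg 30% | Treg 30 to 21 | 6.0 × 0.7/0.5 = 8.4% (rise) |
| (c) CD3 50%, CD4 40% | CD4 500 to 300 | 55.6 × 0.6/0.5 = 66.7% (rise) |
| (d) CD4 50%, Treg 70% | Treg 30 to 9 | 6.0 × 0.3/0.5 = 3.6% (fall) |
| (e) CD4 30%, Treg 60% | Treg 30 to 12 | 6.0 × 0.4/0.7 = 3.4% (fall) |

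The loss is hidden in (a), its direction is reversed in (b) and (c), and its direction is kept in (d) and (e).

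**3. Does the CBC recover the count?** Cells/µL = subset as a fraction of CyTOF lymphocytes × absolute lymphocyte count. In (b), take lymphocytes as falling 50%, to 600. Baseline is 30/1200 = 2.5%, and 2.5% × 1200 = 30. Follow-up is 21/600 = 3.5%, and 3.5% × 600 = 21. The 30% loss reappears. Any proportional error in the lymphocyte count passes straight into the result.

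**4. Which draws, and how well are they matched?** Appendix E lists the CyTOF (ACD) tubes at baseline, C1D1, C1D15, C2D1, C2D15, C3D1 and C3D15; C4D1 has none. Draws precede dosing, so C1D1 is untreated and 6 − 1 = 5 draws after baseline are on treatment. (Section 2.4.2.1 speaks of 24 weeks; Sections 9.1 and 13.5 and Appendix E stop at 12, which I follow.)

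At C1D1 and later visits the CBC and the correlative draw share a 72-hour window. The baseline samples do not. Baseline labs may be 14 days before registration, and treatment should start within 7 days after it, so that CBC may be 14 + 7 = 21 days before the first dose. The baseline correlative draw can fall anywhere in the 14 days before treatment. The C1D1 pair is therefore the better reference.

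**The case against.** The strongest reply is that this is exploratory work, reported descriptively, with no decision attached, and that the CBC is collected anyway, so counts could be derived later. Several parts of that case stand.

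- **A general lymphocyte fall would not be missed.** A reader might infer that it would be reported as no immune effect. The documents do not support that. The CBC with differential is taken before each dose, a low lymphocyte count is a listed adverse event for both drugs, and Section 13.4.3.1 tabulates maximum grade by arm. What is missing is the breakdown by subset: the calendar's laboratory list contains no CD4 or Treg count.
- **Reversal is possible, not shown.** A reader might infer that the plan will invert the varlilumab signal. That needs the parent to fall faster than the subset. For varlilumab alone the protocol cites a Treg reduction and no CD4 fall, which, if preferential, is the case where percent of parent keeps its direction. The CD4 fall is cited only for the combination. The documents do not say whether the earlier falls were counts or percentages, or how large they were.
- **A derived count has its own error.** It combines a separated, frozen sample with a CBC from another tube, and same-occasion drawing is permitted rather than required. Percentages within a lineage depend less on those steps. For marker expression within a subset, such as PD-1 or TIM-3, a percentage is the natural scale.

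These points argue against making counts the main readout. They do not argue against adding counts. Deriving them later without a stated rule would leave the pairing and the reference sample to be chosen after the data are seen.

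**Conclusion.** The gap is real and modest. Percent of parent is the only unit stated for blood subsets. That it is the only one is read from the absence of any other, not from an explicit restriction. On that scale the planned tests cannot separate depletion from altered composition when the parent also falls, and the protocol gives reason to expect that it may.

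The size cannot be fixed from the documents. Under the assumed falls of 30% to 70%, a true Treg loss appears as 6.0% unchanged, as a rise to 8.4%, or as a fall to between 3.4% and 3.6%, depending only on how far CD4 falls alongside. The illustration shows what can happen and does not predict what will. The issue touches the five on-treatment draws and the exploratory analyses built on them. It does not touch the response-rate comparison or any secondary endpoint. It is a cheap improvement to the answer to objective 1.3.1.

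**What to change.** In the peripheral blood bullet of Section 13.5, with a matching line in Section 2.4.2.1:

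- Keep percent of parent, and add derived cells per microlitre for blood lymphoid subsets.
- Define the count as the subset's fraction of CyTOF lymphocytes times the absolute lymphocyte count from the CBC with differential at the same pre-dose visit. Prefer a same-day draw and record the interval where it is not. State the lymphocyte gate; the Appendix F panel includes CD45, CD3, CD19 and CD56.
- Use the pre-dose C1D1 pair as the baseline reference.
- Run the planned paired tests and outcome associations on both scales for C1D15, C2D1, C2D15, C3D1 and C3D15.
- Say that the count is a companion to percent of parent and not a replacement, because it carries extra error from separation, freezing and CBC timing.

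The cost is a few lines of analysis-plan text, one merge of scheduled data and roughly twice the output for this measure. No extra blood or assay is needed. Before adopting it, confirm that the differential values are captured in the trial database.
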